6 STUDY DESIGN

6.1 DESCRIPTION OF THE STUDY

This is a multicenter, multinational, open-label, randomized, active-controlled, 2-arm parallel group comparative Phase 3 study which will recruit outpatients with T1DM or with T2DM (in the US only) of at least one year (12 months) duration and who have been on MDI regimen using insulin glargine (100 U/mL) in the last 6 months prior to screening visit or Levemir (insulin detemir) in the last 12 months prior to screening visit and NovoLog/NovoRapid or insulin lispro 100 U/mL in the last 6 months prior to screening visit, comparing:

- Insulin glargine 100 U/mL (Lantus) in combination with SAR341402.
- Insulin glargine 100 U/mL (Lantus) in combination with NovoLog/NovoRapid.

The study is open-label as injection devices, leaflets and other training material, and treatment kits are distinguishable from each other.

The protocol-mandated background therapy is the insulin glargine (Lantus), which will be continued throughout the study, including the comparative safety extension period.

Approximately 580 patients will be randomized to the rapid-acting insulins SAR341402 or NovoLog/NovoRapid in a 1:1 ratio at the end of the screening period.

- Approximately 250 patients with T1DM will be randomized in the geographical area using NovoRapid (including Europe and Japan).
- Approximately 330 patients, including 230 with T1DM and 100 with T2DM, will be randomized in the geographical region using NovoLog (all in the US).

The number of patients with T1DM expected to be randomized in the US versus outside of the US may change owing to the recruitment potential at those regions.

Randomization will be stratified by geographical region (Europe, US, Japan), by type of diabetes (T1DM, T2DM [T2DM only for US]), by HbA1c obtained at the screening visit (<8.0%, ≥8.0%), and by prior use of NovoLog/NovoRapid (Yes, No).

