10 STUDY PROCEDURES

10.1 VISIT SCHEDULE

The visit schedule and procedures/assessments listed in the "Study Flow Chart" (Section 1.2) are not repeated in this section. The aim of this section is to provide details on how some of the procedures/assessments have to be performed.

This is an outpatient study and consists of 8 on-site visits and 5 phone-call visits. Additional, optional phone call visits to monitor and support the progress of insulin titration should be scheduled whenever considered necessary by the Investigator.

All on-site visits should take place in the morning. The patients must be fasting for Visit 1 (Week -2, screening), Visit 3 (Day 1, baseline), Visit 7 (Week 12), Visit 9 (Week 26, Endpoint), Visit 11 (Week 40), and at end of treatment assessment Visit 12 (Week 52) or at early discontinuation from IMP. Patient is required to come to the visit after a fasting period of at least 8 hours: during this time, only water or tea without sugar or sweetener and without milk is allowed. No coffee, no other beverages; no injection of rapid-acting insulin at home are allowed. Patients do not need to come to other on-site titration visits fasting.

Eight-hour delay must be respected between the last mealtime insulin dose and AIA sampling time for Visit 3 (Day 1, baseline), Visit 5 (Week 4), Visit 7 (Week 12), Visit 9 (Week 26 Endpoint), Visit 11 (Week 40) and at end of treatment assessment Visit 12 (Week 52) or at early discontinuation from IMP.

Visit window: Visit 2 should take place 7 days ±3 days after Visit 1 (screening). Visit 3 should occur 14 days ±3 days after Visit 1 (screening). From Visit 4 (Week 2) until the primary efficacy endpoint visit (Visit 9, Week 26), visits should occur within ±3 days, taking the baseline (Visit 3) visit day as a reference. Visits in the extension period, phone visit (Visit 10, Week 34), and on site visits (Visit 11, Week 40) to end of treatment (Visit 12, Week 52) may occur within ±5 days. Post treatment follow-up visit, (Visit 13, Week 52+1 day) may occur at +2 to 3 days in the event this visit falls on a weekend or holiday.

If one visit date is changed, the next visit should occur according to the original schedule.

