10.1.1.1 On-site Visit 1 (Week -2) screening visit

The following procedures/assessments will be performed at the Visit 1 (Week -2):

- Obtaining the informed consent:
 - The patient will receive verbal information concerning the aims and methods of the study, its constraints and risks and the study duration. Written information will be provided to the patient. Written informed consent must be signed by the patient and Investigator prior to any study-specific investigations.
- IRT notified (allocation of patient number, registration of screening, collection of demographic information):
 - The patient number is composed of a 12-digit number containing the 3-digit country code, the 4-digit center code and the 5-digit patient chronological number (which is 00001 for the first patient screened in a center, 00002 for the second patient screened in the same center etc).
- Assessment of inclusion/exclusion criteria.
- Demographics (age, gender, and ethnic origin).
- Patient's medical (including detailed cardiovascular) and surgical history as well as family history of diabetes in the immediate family.

- History of T1DM or T2DM treatment including documentation for diagnosis, of insulin treatment (including start date of first insulin treatment), documentation of current treatment and treatment in the last 6 months with insulin glargine (in the last 12 month with insulin detemir) and insulin lispro or NovoLog/NovoRapid (including start dates), duration, and of microvascular complications (eye, kidney) and their treatments, all of which must be in the source documentation prior to randomization.
- History of T1DM or T2DM, supporting documentation for diagnosis, must be in source documentation prior to randomization.
- Concomitant medication history.
- Habits: alcohol habits and smoking status (during the last 12 months).
- Physical examination.
- Body height and weight, vital signs (determination of reference arm for BP; SBP, DBP, heart rate).
- 12-lead ECG.
- Laboratory testing by central laboratory:
 - HbA1c,
 - Safety laboratory test for hematology, clinical chemistry (please refer to Section 9.2.3.2.3),
 - Serum lipids (please refer to Section 9.2.3.2.3),
 - Hepatitis serology (HBs-Ag, HC-Ab),
 - Serum pregnancy test (β-human chorionic gonadotropin [β-HCG]) in WOCBP only,
 - FSH and estradiol in postmenopausal women only.
- Report AE/SAE, hypersensitivity reactions and hypoglycemia if any.
- E-diary and Sponsor provided glucometer dispensation:

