10.1.2.1 Baseline visit (Visit 3, Week 0/Day 1)

Patients meeting all inclusion criteria and with no exclusion criteria at the end of the screening period (based on data collected at the screening Visit 1 [Week -2], at Visit 2 [Week -1] [if applicable] and Visit 3 [Week 0]) are eligible to be randomized and can participate in the study. Patients must have demonstrated the ability and willingness to use the e-diary during the screening period.

For the complete list of procedures scheduled for this visit, please refer to the study flowchart (Section 1.2) and for detailed description of assessments (Section 9.2.2.2, Section 9.2.3.2).

At this visit, the patient must return to the investigation site in the morning after an overnight fast (no less than 8 hours fasting) and not having injected their mealtime insulin at home. Eight-hour delay between injection of insulin lispro or insulin aspart and AIA sampling must be respected.

Patients will come with the sponsor provided glucometer and the e-diary.

- Body weight, vital signs (SBP and DBP, heart rate).
- Laboratory testing done by central laboratory:
 - HbA1c,
 - FPG.
 - AIA,
 - C-peptide.
- Urine pregnancy test in WOCBP.
- Concomitant medications are reviewed.

- Patient e-diary is verified to ensure that no pending data are stored in the e-diary and if so, data should be transmitted. The e-diary data is reviewed in the vendor web portal by the Investigator or SubInvestigator who are qualified and familiar with the study and the following is validated in the clinical database:
 - On at least 2 days in the week before the baseline visit (Visit 3): 7-point plasma glucose profile (fasting prebreakfast, 2 hours postbreakfast, pre- and 2 hours after lunch, pre- and 2 hours after dinner, and at bedtime) measured in a single, 24-hour period,
 - All doses of NovoLog/NovoRapid or insulin lispro injected either prior to meal intake or immediately after meal intake, including any corrective dose related to the SMPG on each day of the week prior to the baseline visit,
 - Doses of insulin glargine or insulin detemir 100 U/mL on each day of the week prior to the baseline visit,
 - Any SMPG related to hypoglycemia and symptoms of hypoglycemia.
- Patients will be reminded to record daily dose of IMP and NIMP, including any corrective dose related to the SMPG on each day of the week after the baseline visit.

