1.4 STUDY PLAN

The following figure describes the design of the study:

Figure 1 - Study design

The study consists of:

- A 2-week screening period, from signed informed consent to randomization.
- A 26-week treatment period, from randomization to Visit 9 (Week 26).
- A 26-week comparative safety extension period, from Visit 9 (Week 26) to the end of treatment visit (Visit 12, Week 52).
- A 1-day follow-up period with a safety telephone visit 1 day after the end of treatment visit.

In total, the study duration will be 54 weeks per patient (+ 1 day safety follow-up).

The end of treatment is at Visit 12 (Week 52) after randomization. The end of the study is a follow-up contact (Visit 13) at the time of Week 52 plus 1 day.

In case of premature permanent investigational medicinal product (IMP) discontinuation, patients will have as soon as possible a premature treatment discontinuation visit (recorded as Visit 8000 in the clinical database) with the assessments normally planned at Visit 12 (Week 52), followed by a safety follow-up (recorded as Visit 8010 in the clinical database) 1 day after.

Afterwards, the patients will remain in the study until at least Visit 9 (Week 26), and will be followed-up according to the visits and assessments as planned in the protocol (except for the 1-day safety post-treatment follow-up [Visit 13]).

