2.1.4.1 Hypoglycemia

All hypoglycemia will be reported by patient in e-diary, transferred to the dedicated hypoglycemia event page in the e-CRF and reviewed by the investigator in specific items, or directly completed in another dedicated hypoglycemia event page in the e-CRF by the investigator. For the analyses, the investigator items will be used when available.

All hypoglycemia will be categorized according to the ADA definitions (3) as described below:

- Severe hypoglycemia: Severe hypoglycemia will be derived as an event requiring assistance of another person to actively administer carbohydrate, glucagon, or other resuscitative actions.
- **Documented symptomatic hypoglycemia:** Documented symptomatic hypoglycemia will be derived as an event with symptoms of hypoglycemia and with a measured plasma glucose concentration less than or equal to 3.9 mmol/L (70 mg/dL).
- Asymptomatic hypoglycemia: Asymptomatic hypoglycemia will be derived as an event without symptoms of hypoglycemia but with a measured plasma glucose concentration less than or equal to 3.9 mmol/L (70 mg/dL).
- **Probable symptomatic hypoglycemia:** Probable symptomatic hypoglycemia will be derived as an event with symptoms of hypoglycemia and missing plasma glucose concentration.
- **Relative hypoglycemia:** Relative hypoglycemia (recently termed "pseudohypoglycemia") will be derived as an event with symptoms of hypoglycemia but with a measured plasma glucose concentration greater than 3.9 mmol/L (70 mg/dL).

Any technical details to categorize hypoglycemia in case of missing hypoglycemia information are described in Section 2.5.3.

Hypoglycemia will be evaluated regardless the time of onset during the day.

In addition to the threshold of plasma glucose of less than or equal to 3.9 mmol/L (70 mg/dL), documented symptomatic hypoglycemia and asymptomatic hypoglycemia with a measured plasma glucose concentration less than 3.0 mmol/L (54 mg/dL) will also be analyzed.

Hypoglycemia observation period

- Pre-treatment hypoglycemia are events that occurred during the pre-treatment period.
- Treatment-emergent hypoglycemia are events that occurred during the on-treatment period (see Section 2.1.4).
- Post-treatment hypoglycemia are events that occurred during the post-treatment period.

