- For any hypoglycemia, severe and documented symptomatic hypoglycemia category, number and rate of hypoglycemia per patient-year will be compared for SAR341402 versus NovoLog/NovoRapid using an overdispersed Poisson regression model with a log-link function, and the logarithm of the treatment-emergent period as offset (using PROC GENMOD). The dispersion parameter will be estimated by Pearson's chi-square statistic divided by its degrees of freedom (option SCALE=PEARSON). The model will include fixed-effect terms for treatment group and randomization strata of geographical region and type of diabetes (Europe T1DM, US T1DM, US T2DM, Japan T1DM), screening HbA1c (<8%, ≥8%), and prior use of NovoLog/NovoRapid (Yes, No). If a model does not converge (eg, due to sparse data), the randomization strata may be adapted or removed from the model. Rate ratios and 95% CIs will be displayed using forest plots.

• For any hypoglycemia, severe and documented symptomatic hypoglycemia category, the number and rate of hypoglycemia per patient-year will be presented by subgroup type of comparator (NovoLog, NovoRapid) and compared between SAR341402 and NovoLog/NovoRapid using a similar overdispersed Poisson regression model as described above. If a model does not converge (eg, due to sparse data), the randomization strata may be adapted or removed from the model. Rate ratios and 95% CIs will be displayed using forest plots.

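### The hypoglycemia rate model leaves out each patient's recorded pre-treatment hypoglycemia; adjusting for it, with a robust variance, is a cheap and possibly useful gain in precision for the two frequent event categories.

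*SAP*

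**What the plan says.** **The model.** For any, severe and documented symptomatic hypoglycemia, SAP 2.4.5.1 compares rates with an "overdispersed Poisson regression model with a log-link function, and the logarithm of the treatment-emergent period as offset". The dispersion is the Pearson chi-square over its degrees of freedom. On covariates it says: "The model will include fixed-effect terms for treatment group and randomization strata of geographical region and type of diabetes". Screening HbA1c category and prior NovoLog/NovoRapid use complete the list. The output is rate ratios with 95% CIs in forest plots, for the 6- and 12-month periods, in all patients and in T1DM patients, and again by comparator (NovoLog or NovoRapid).

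**The unused data.**
- Protocol 10.1.1.1 dispenses the e-diary at Visit 1 and asks sites to do the following: "Report AE/SAE, hypersensitivity reactions and hypoglycemia if any".
- Protocol 10.1.1.2 has hypoglycemia reviewed in the diary portal at Visit 2.
- Protocol 10.1.2.1 lists among the diary data validated in the clinical database at Visit 3: "Any SMPG related to hypoglycemia and symptoms of hypoglycemia".
- SAP 2.1.4.1 names the variable: "Pre-treatment hypoglycemia are events that occurred during the pre-treatment period". SAP 2.4.5.1 then analyzes on-treatment events only.

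**Status of the comparison.** Protocol 11.4.3.1 calls the rate ratios exploratory and optional. SAP 2.4.5 describes the safety analyses as essentially descriptive, without systematic testing.

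**The concern.** If patients differ in their underlying tendency to hypoglycemia, a model that knows nothing about that tendency treats the differences as noise. They enter the Pearson dispersion factor and widen every interval. A patient's own run-in count carries some information on it. The SAP follows this logic for HbA1c, where the ANCOVA in 2.4.4.1.1 includes the baseline value of the outcome, but not for hypoglycemia rates.

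No formal test is attached to these rate ratios, so the width of the interval carries the interpretation. Precision is scarcest in the comparator subsets, planned at about 330 (NovoLog) and 250 (NovoRapid) patients. With a log link, adjusting for a baseline covariate does not change which rate ratio is estimated.

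**Working it through.** **The plan's own figures.** The documents give no power, precision, event rate, dispersion or within-patient correlation for hypoglycemia, so there is nothing to reproduce on this point. The HbA1c power does reproduce (290 per arm, SD 1.0, margin 0.3, one-sided 0.025: 95.1% against a stated minimum of 95%), but it has no bearing here.

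**Inputs from the documents.** 290 patients per arm; run-in of 14 days, give or take 3 (Protocol 10.1), so 11 to 17 days; 182 days on treatment in the main period; quasi-Poisson model with Pearson scale.

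**Assumed inputs.** Event rate 5, 20 or 60 per patient-year; variance V of a mean-1 log-normal patient rate multiplier, 0.5 to 2; correlation of the patient's log rates before and on treatment, 0.6 to 0.9. The randomization strata and dropout are not modelled.

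**Expected counts per patient** (rate × days / 365.25):
- 5 per year: 0.19 in a 14-day run-in, 2.5 on treatment
- 20 per year: 0.77 and 10.0
- 60 per year: 2.3 and 29.9

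**Check of the unadjusted SE.** SE² ≈ (2/290) × (1/μ + V), where μ is the expected on-treatment count. At 60 per year and V = 1: (2/290) × (1/29.9 + 1) = 0.00713, so SE = 0.084. The simulation gives the same model SE.

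**Effect of adding log(run-in count + 0.5).**

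| Rate per patient-year | Fall in Pearson-scaled SE | Fall in true (empirical) SE |
|---|---|---|
| 5 | 1-15% | about 0-5% |
| 20 | 5-32% | 3-21% |
| 60 | 10-45% | 7-33% |

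The last column uses 800 trials per scenario and an 11-17 day run-in. A run of 1,500 trials gave 0-8% in the top row and the same ranges below it, so the top row carries some Monte Carlo uncertainty.

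**Why the two columns differ.** After adjustment the Pearson-scaled SE understates the real sampling error.
- At 60 per year, V = 1, correlation 0.9, the Pearson SE falls from 0.084 to 0.056 (33%). The empirical SE falls from 0.086 to 0.064 (26%). In a 2,000-trial run of this scenario, coverage of the 95% CI went from 94.2% to 91.7%.
- At 60 per year, V = 2, correlation 0.9, the Pearson SE falls 44% and the true SE 32%, with coverage 88.7%. The lowest coverage in any run was about 88%.
- The unadjusted model covered 94.2-94.8%. The adjusted model with a robust (sandwich) variance covered about 93-96%.

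On the ratio scale, for an estimate of 1 in the V = 1 example, the interval exp(±1.96 × 0.086) is 0.84 to 1.18. With exp(±1.96 × 0.064) it is 0.88 to 1.13.

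**Sensitivity to the correlation.** In a second grid (14-day run-in, 10 to 60 events per patient-year, 400 trials per scenario) the true SE fell by 0-4% at correlation 0.4, 3-14% at 0.7 and 5-44% at 1.0.

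**Severe events.** At 0.05 to 0.3 per patient-year only about 0.2-1.2% of patients have any run-in event (for example 0.3 × 14 / 365.25 = 1.15%). The model SE falls by 0-2%, and at 0.05 to 0.1 per year some adjusted fits become unstable.

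**The case against.** The strongest answer is that nothing here is broken. Randomization makes the planned comparison valid without the covariate. Adjusting for the strata is a consistent, prespecified choice that matches the logistic models in the same section. No margin, power or decision rule depends on the width of these intervals. All of this stands.

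The correlation may also be low. During the run-in, patients are learning a new glucometer and e-diary and are still on pre-study insulins, which may be lispro or detemir. From randomization they switch insulin, titrate to targets with daily glucose testing recommended in the first weeks, and, if they have T2DM, stop sulfonylureas. Detection and regimen both change, so a correlation near 0.4, and with it a gain of 0-4%, cannot be excluded. This stands as a limit on the size of the gain, not as a reason against the covariate. Missing run-in data should be limited, because E 24 in Protocol 7.2.3 excludes patients unwilling or unable to use the diary.

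A reader might infer that the trial's main safety comparison is compromised. The documents do not support that: they designate no main safety comparison, and Protocol 9.5 names hypoglycemia as one of several parameters of special interest. A reader might also infer that the gain is free and as large as the Pearson-scaled figures suggest. Part of that narrowing is false precision, so adding the covariate under the existing Pearson scale would replace approximately valid intervals with intervals that are too short.

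**Conclusion.** The point holds as an efficiency improvement for any and documented symptomatic hypoglycemia. The plan collects, validates and defines pre-treatment hypoglycemia and then omits it from the rate model. Using it costs no new data, left the rate ratio unbiased in simulation, and never materially lost precision for these frequent categories.

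The gain ranges from negligible, when events are infrequent or the correlation is weak, to roughly a third of the true SE when events are frequent and the correlation is high. Where this trial falls in that range cannot be read from the documents. The result rests on the assumed rates, variances and correlations and on log-normal patient effects.

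The point does not extend to severe hypoglycemia, where there is almost no run-in information. Nor does it extend to the logistic models, where adjustment changes the meaning of the odds ratio.

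**What to change.** Before the 6-month database lock, when treatment allocation enters the sponsor's database (Protocol 8.3.1), amend the rate model in SAP 2.4.5.1 for any and documented symptomatic hypoglycemia only:

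1. Add log(pre-randomization event count of the same category + 0.5) and log(run-in days) as covariates, or a single log run-in rate. Count from diary dispensing at Visit 1 and stop at randomization. The SAP's pre-treatment period runs to the first injection, and events after randomization could be affected by knowledge of the assigned arm.
2. Take the 95% CI from a robust (sandwich) variance in place of SCALE=PEARSON.
3. State a rule for missing run-in diary data.
4. Leave the severe-event rate model and all logistic models as they are.

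If the sponsor prefers to keep the current model as the main presentation, the adjusted model can be a prespecified sensitivity analysis.

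The cost is a few lines of specification (zero counts, run-in length, missing diaries, variance estimator) and a covariate set that differs between the frequent-event and severe-event models in the same forest plots. No visits, patients or data are added.

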2.4.5.2 Analyses of adverse events

Generalities

The primary focus of adverse event reporting will be on treatment-emergent adverse events. Pretreatment and posttreatment adverse events will be described separately. Analyses will be presented separately for the main 6-month and the 12-month on-treatment periods.

If an adverse event date/time of onset (occurrence, worsening, or becoming serious) is incomplete, an imputation algorithm will be used to classify the adverse event as pretreatment, treatmentemergent, or posttreatment. The algorithm for imputing date/time of onset will be conservative and will classify an adverse event as treatment emergent unless there is definitive information to determine it is pretreatment or posttreatment. Details on classification of adverse events with missing or partial onset dates are provided in Section 2.5.3.

Adverse event incidence tables will present by SOC, HLGT, HLT, and PT, sorted in alphabetical order for each treatment group, the number (n) and percentage (%) of patients experiencing an adverse event. Multiple occurrences of the same event in the same patient will be counted only once in the tables within a treatment phase. The denominator for computation of percentages is the safety population within each treatment group.

Sorting within tables ensures the same presentation for the set of all adverse events within the observation period (pretreatment, treatment-emergent, and posttreatment). For that purpose, the table of all treatment-emergent adverse events presented by SOC and PT sorted by the internationally agreed SOC order and decreasing frequency of PTs within SOCs will define the presentation order for all other tables unless otherwise specified. Sorting will be based on results for the SAR341402 treatment arm.

Analyses of all TEAE(s) will be generated for the safety population and for the T1DM patients (except for analyses by subgroup).

Analysis of all TEAE(s)

- Overview of TEAEs, summarizing number (%) of patients with any
 - TEAE,
 - serious TEAE,
 - TEAE leading to death,
 - TEAE leading to permanent treatment discontinuation.

- All TEAEs by primary SOC, showing number (%) of patients with at least one TEAE, sorted by internationally agreed order of primary SOC.
- All TEAEs by primary SOC, HLGT, HLT, and PT, showing number (%) of patients with at least one TEAE sorted by SOC internationally agreed order. The other levels (HLGT, HLT, PT) will be presented in an alphabetic order.
- Number (%) of patients experiencing TEAE(s) presented by PT, sorted by decreasing incidence of PT.
- All TEAEs by primary SOC and PT, showing number (%) of patients with at least one TEAE, sorted by SOC internationally agreed order and decreasing incidence of PTs within SOC. This sorting order will be applied to all other tables, unless otherwise specified.
- Number (%) of patients experiencing common TEAE(s) (HLT incidence ≥2% in any treatment group) presented by primary SOC, HLT, and PT, sorted by SOC internationally agreed order. The other levels (HLT, PT) will be presented in an alphabetic order. Analysis performed overall and by subgroup. The following subgroups will be displayed:
 - Race (American Indian or Alaska Native, Asian, Black or African American, Native Hawaiian or Other Pacific Islander, White, More than One Race, Unknown or Not Reported),
 - Ethnicity (Hispanic or Latino, Not Hispanic or Latino, Unknown /Not Reported),
 - Age group (<65, \geq 65 to <75, \geq 75 years of age),
 - Sex (male, female),
 - Baseline BMI ($<30, \ge 30 \text{ kg/m}^2$),
 - Baseline estimated GFR categories ($<60, \ge 60 \text{ mL/min}/1.73 \text{ m}^2$),
 - Randomization stratum of type of diabetes (T1DM, T2DM),
 - Randomization stratum of screening HbA1c (<8%, $\geq8\%$),
 - Randomization stratum of prior use of NovoLog/NovoRapid (Yes, No),
 - Type of comparator (NovoLog, NovoRapid),
 - Regions (North America, Western Europe, Eastern Europe, ROW),
 - Duration of diabetes ($<10, \ge 10$ years).
- All TEAEs regardless of relationship and related to IMP by primary SOC, HLGT, HLT, and PT, showing number (%) of patients with at least one TEAE, sorted by SOC internationally agreed order. The other levels (HLGT, HLT, PT) will be presented in an alphabetic order.
- All TEAEs by maximal severity, presented by primary SOC and PT, showing number (%) of patients with at least one TEAE by severity (ie, mild, moderate, or severe), sorted by the sorting order defined above.

• Number (%) of patients experiencing TEAE(s) presented by Primary and Secondary SOC, HLGT, HLT, and PT, sorted by SOC internationally agreed order. The other levels (HLGT, HLT, PT) will be presented in an alphabetic order.

Analysis of all treatment-emergent SAE(s)

- All treatment-emergent SAEs by primary SOC, HLGT, HLT, and PT, showing number (%) of patients with at least one serious TEAE, sorted by SOC internationally agreed order. The other levels (HLGT, HLT, PT) will be presented in an alphabetic order.
- All treatment-emergent SAEs regardless of relationship and related to IMP by primary SOC, HLGT, HLT, and PT, showing number (%) of patients with at least one treatment-emergent SAE, sorted by SOC internationally agreed order. The other levels (HLGT, HLT, PT) will be presented in an alphabetic order.

Analysis of all TEAE(s) leading to treatment discontinuation

• All treatment-emergent adverse events leading to treatment discontinuation, by primary SOC, HLGT, HLT, and PT, showing the number (%) of patients sorted by the internationally agreed SOC order. The other levels (HLGT, HLT, PT) will be presented in alphabetical order.

Analysis of TEAE(s) related to injection site reactions and hypersensitivity reactions

- All TEAEs related to injection site reactions, hypersensitivity reactions, or events confirmed as allergic reactions by ARAC, by PT, showing number (%) of patients sorted by decreasing incidence of PT in the SAR341402 group.
- All TEAEs related to injection site reactions, hypersensitivity reactions, or events confirmed as allergic reactions by ARAC, regardless of relationship and related to IMP, by PT, showing number (%) of patients sorted by decreasing incidence of PT in the SAR341402 group.
- A summary and/or listing of all events adjudicated by ARAC will be provided with the result of the adjudication.

Analysis of adverse events of special interest

• A listing of patients with symptomatic overdose with IMP/NIMP will be provided.

Analysis of pretreatment and posttreatment adverse events

• A listing of all pre-treatment and post-treatment AEs will be provided.

